TITLE: Randomized Clinical Trial Comparing Analgesia and Plasma Pharmacokinetics of Lidocaine administered by Erector Spinae Plane Blocks vs. Intravenous Routes Following Open Heart Surgery: An Equivalence Study

NCT Number: NCT04995497

[name]

Document Date: April 13, 2022

Protocol Outline

[figure not shown]
Protocol Title: Randomized Clinical Trial Comparing Analgesia and Plasma Pharmacokinetics of Lidocaine Administered by Erector Spinae Plane Blocks vs. Intravenous Routes Following Open Heart Surgery: An Equivalence Study

Protocol Version: 5

Protocol Date: April 13, 2022

Principal Investigator: [name]

Research Team: [name] [name]

I. Abstract

Recently interfascial plane blocks have been developed for analgesia including erector spinae plane (ESP) block. The ESP block has been hypothesized to provide truncal analgesia by spread of local anesthetic into the paravertebral space. However, recent studies have shown that the spread of local anesthetic by this block procedure into the paravertebral space is unreliable. It has been established that interfascial plane blocks can result in systemic levels of local anesthetic that can achieve therapeutic concentrations similar to those observed by intravenous infusions of local anesthetic and could likely be the mechanism of action of the ESP block. Free and total plasma lidocaine levels will be measured until steady state levels are achieved with ESP blocks. Additionally, the safety of the ESP block using doses of local anesthetic has not been rigorously evaluated. This study will evaluate both the analgesic efficacy and safety of ESP blocks in post-cardiac surgery

patients in comparison to intravenously administered lidocaine.

II. Background and Significance/Preliminary Studies

Postoperative pain is a significant issue following open heart surgery and poorly controlled pain can result in significant cardio-respiratory morbidity. A significant number of patients suffer from pain issues both at rest (49%) and on movement (62%) following open heart surgery via sternotomy (1,2) and adequate pain management requires closer re-assessment and treatment. The intensity of pain is noted to be higher in the first 48 hours post-surgery (3,4,5,6,7,8) and hence modalities to control pain may make the greatest difference in the first two days after surgery.

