It is well known that interfascial plane blocks can result in systemic levels of LAs that achieve therapeutic concentrations (15) similar to that observed by intravenous infusions of LA (16,17). This is very likely the case for the ESP block, especially since the clinical and anatomical studies have conflicting findings regarding the loco-regional effects. Although intravenous lidocaine has shown some promise to prevent post-operative cognitive dysfunction (18,19), its effect on postoperative pain is not well studies. One study utilizing low dose lidocaine failed to show improvement in pain scores or opioid consumption, but the study did not utilize standardized multimodal analgesia

regimen (20). It is currently unknown whether the analgesic benefits of interfascial plane blocks are due to the multimodal analgesic regimen, the loco-regional benefits of the blocks, the systemic levels of local anesthetics following the block performance or a combination of all. We hypothesize that the mechanism by which the ESP block produces analgesia in the background of multimodal analgesia is probably related to the systemic absorption of local anesthetics. In addition, the safety of the ESP block using high doses of LA in cardiac surgery patients has not been rigorously assessed. We propose a pragmatic study to address both unknowns, the mechanism and safety of ESP following cardiac surgery.

III. Study Aims

- 1. The hypothesis of this study is that the analgesic effects of ESP can be attributed to its systemic distribution rather than its locoregional effects. A finding that lidocaine administered by ESP block achieves plasma concentrations in the analgesic range (2-5 ug/ml) at steady state will support our hypothesis whereas inability to reach analgesic levels will suggest that systemic distribution of local anesthetic is not a significant contributing factor of analgesia.
- 2. Despite the use of clinically acceptable doses, plasma concentrations of local anesthetic have been known to reach toxic levels following bilateral paravertebral blocks. This may also be true of ESP blocks. This study will address this concern and help establish a safety profile for ESP blocks in the cardiac patient population.

IV. Administrative Organization

University of Iowa Hospitals and Clinics—CVICU and Laboratories

V. Study Design

- i. Experimental design of the study (e.g., single-blind, double-blind): Randomized

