- ii. Study population general description: Adults undergoing elective cardiac surgery for coronary artery bypass graft (CABG) or valve surgery via sternotomy
- iii. Sample size determination and power analyses: 70 adult patients as determined using an online calculator available at: https://www.sealedenvelope.com/power/continuous-equivalence/
- iv. Study outcomes/endpoints:
 - 1. Arterial blood samples will be drawn and assessed for lidocaine concentrations
 - 2. Pain scores will be collected from EPIC electronic medical record or directly from the subjects.
 - 3. Opioid doses will be assessed and reported in morphine equivalents

VI. Study Procedures

- a. Subject selection procedures
 - i. Inclusion: Any patient >18 years and <81 years undergoing elective cardiac surgery for CABG or valve surgery via sternotomy and surgical procedure is not greater than 12 hours

Exclusion: Allergy to study medications; major livor or kidney dysfunction; BMI <20 or >50; revision surgery; Off-pump coronary artery bypass surgery; surgery via thoracotomy; narcotic dependent (opioid intake morphine equivalent > 10 mg/day for more than 3 months); other sources of chronic pain such as fibromyalgia; patients with associated significant central nervous system, liver, renal or respiratory disease; coexisting hematological disorder or deranged coagulation parameters; lack of informed consent; preoperative neurological deficits; and emergency surgery (E1, E2 and E3 classifications only).

ii. Recruitment procedures

- **1. Where will recruitment occur?** Pre-surgical clinic or Day of Surgery Admissions (DOSA)
- **2.** Where and when will consent be obtained? DOSA prior to surgery or in pre-surgical clinic
- 3. Who will obtain consent? Anesthesia team
- 4. What is the advertising plan, if applicable? N/A
- 5. What recruitment materials will be provided to the potential participant (brochures/information sheets/video presentation)? None.

iii. Screening procedures

- 1. What procedures are required for screening? Prior to the surgical procedure, the anesthesia team will review eligibility criteria: Allergic to study medication; diagnosed with major liver or kidney dysfunction; any bleeding disorders; in females verify non-pregnant state.
- 2. What is the screening schedule (number of visits, length of visits)? This will occur only on the day of surgery and will last approximately 30 minutes.

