If an adverse/serious adverse event occurs, the study will be paused until careful evaluations is performed.

VIII. Analysis Plan

Study variables will be collected and tabulated. The continuous and discrete variables will be presented as mean and standard deviation after calculation and the categorical variables will be presented as frequencies. Normality of distribution will be assessed using Q-Q plots followed by Shapiro-Wilk test. Normally distributed data will be assessed using independent sample t-test and non-normally distributed data will be assessed using Mann-Whitney U-test. Categorical variables will be tested using chi-square tests or Fisher's exact test. Tests for equivalence will be applied for the primary outcome measures

failing which, tests of superiority will be applied. P values <0.05 will be considered statistically significant.

IX. Literature Cited

- 2. LahtinenP, Kokki H, Hynynen M. Pain after cardiacsurgery: A prospective cohort study of 1-year incidence and intensity. Anesthesiology. 2006;105 (4):794–800. doi:10.1097/00000542-200610000-00026
- 5. Reimer-Kent J. From theory to practice: preventing pain after cardiac surgery. Am J Crit Care. 2003;12(2):136–143.

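### The trial is titled and sized for equivalence, but the plan names no primary outcome, margin or decision rule from which equivalence could be concluded

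*Combined protocol and SAP*

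**What the plan says.** The title describes a trial "Comparing Analgesia and Plasma Pharmacokinetics of Lidocaine administered by Erector Spinae Plane Blocks vs. Intravenous Routes Following Open Heart Surgery: An Equivalence Study". Section V.iii gives the sample size as "70 adult patients as determined using an online calculator available at" a web address for continuous equivalence outcomes, and reports no inputs. Section V.iv lists lidocaine concentration, pain scores and opioid dose in morphine equivalents, and marks none of them as primary.

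Section VIII first assigns t-tests to normally distributed data, while "non-normally distributed data will be assessed using Mann-Whitney U-test". It then says "Tests for equivalence will be applied for the primary outcome measures", "failing which, tests of superiority will be applied", and ends with "P values <0.05 will be considered statistically significant".

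Two other places bear on the outcome. The Abstract says "Free and total plasma lidocaine levels will be measured until steady state levels are achieved with ESP blocks". Study Aim 1 says "A finding that lidocaine administered by ESP block achieves plasma concentrations in the analgesic range (2-5 ug/ml) at steady state will support our hypothesis". Section VI.d schedules six blood samples (5, 30, 60 and 120 minutes, 6 and 24 hours) and takes pain scores at rest and on movement from charting done every 2 to 4 hours.

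**The concern.** An equivalence conclusion needs a named outcome, a margin fixed in advance, and a rule that compares a confidence interval with that margin. Section VIII announces the test and supplies none of the three. The margin defines the null hypothesis, so without it there is no stated probability of wrongly claiming equivalence. The superiority fallback suffers too: it starts when equivalence fails, and failure is undefined.

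The choices left open are many. There are three unranked outcomes, free and total lidocaine, six sampling times, pain at rest and on movement, and no stated summary for pain or opioid dose. The trial has no placebo, describes no blinding, and leaves the randomization sequence with the principal investigator and research team (VI.b, VI.c). Sealed envelopes protect the assignment before it is made; they do not hide results afterwards. An outcome or margin chosen once results by arm are visible would therefore be open to bias.

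**Working it through.** **Step 1. Look for each element an equivalence test needs.**
- Primary outcome: V.iv lists three and ranks none. Section VIII refers to primary outcomes in the plural and does not identify them.
- Summary and time point: for lidocaine, Aim 1 refers to steady state, but not to which of the six samples represent it or whether free or total drug counts. For pain and opioid dose nothing is given.
- Margin: none. The 2-5 ug/ml range in Aim 1 is an absolute range for the ESP arm, not a limit on the ESP-minus-IV difference.
- SD, power, sidedness, confidence level: none. Section VIII gives 0.05 without saying whether it applies to each one-sided test or is two-sided.
- Decision rule: none. Neither two one-sided tests (TOST) nor an interval rule is stated.

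No redaction mark or gap appears in V.iii or VIII.

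**Step 2. Try to reproduce 70.** For two means with a true difference of zero, the normal approximation is

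n per arm = 2 × [z(1−α) + z(1−β/2)]² / (margin/SD)².

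Margin, SD, α and power are all unstated, so 70 cannot be reproduced forwards. One set that fits is margin 0.70 SD, one-sided α 0.05 and 80% power: 2 × (1.645 + 1.282)² / 0.70² = 34.96 by unrounded z, rounded up to 35 per arm and 70 in total. It is not the only one, as the next step shows.

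**Step 3. Solve backwards.** Assumptions: 1:1 allocation (35 per arm), no loss, zero true difference. Neither the ratio nor a loss rate is stated. Figures in this and the next steps use the exact t distribution, integrating over the pooled variance. The normal approximation is shown once for comparison.

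| One-sided α | Power | Margin, exact t | Margin, normal approx. |
|---|---|---|---|
| 0.05 | 80% | 0.707 SD | 0.700 SD |
| 0.05 | 90% | 0.794 SD | 0.786 SD |
| 0.025 | 80% | 0.786 SD | 0.775 SD |
| 0.025 | 90% | 0.874 SD | 0.862 SD |

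So 70 fits margins from about 0.71 to 0.87 SD, and the intended margin cannot be read off the sample size.

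**Step 4. Power at one-sided 0.05, by margin and evaluable number.** The loss rates are assumed: 10% leaves 31 per arm (35 × 0.9 = 31.5, rounded down) and 20% leaves 28.

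| Evaluable per arm | 0.5 SD | 0.6 SD | 0.7 SD | 0.8 SD | Margin for 80% power |
|---|---|---|---|---|---|
| 35 | 33% | 60% | 79% | 90% | 0.71 SD |
| 31 | 24% | 51% | 72% | 86% | 0.75 SD |
| 28 | 17% | 43% | 65% | 81% | 0.79 SD |

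**Step 5. Effect of the unstated sidedness.** At 35 per arm and a margin of 0.70 SD, power is 79% at one-sided 0.05 and 65% at one-sided 0.025.

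**Step 6. Why a difference test cannot fill the gap (illustration only).** With a true difference of 0.70 SD and 35 per arm, a two-sided 5% t-test is non-significant about 18% of the time. The plan does not propose reading non-significance as equivalence; the figure shows why it should rule that out.

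**The case against.** Much can be said for the plan. Aim 1 gives a numerical criterion in advance for the mechanism hypothesis, and neither aim states between-arm equivalence. Section VII calls the trial a pilot. The calculator must have been given inputs, and dated records outside these documents may hold them, in which case this is a gap in documentation. These points stand as context. They do not supply a margin or a rule, and the title, the sizing method and Section VIII still make an equivalence claim.

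Four stronger readings are tempting, and the documents do not support them.
- *That 70 is too small.* The sample size depends on a margin and SD that are not given, so it can be neither confirmed nor refuted.
- *That a skewed primary outcome will be sent to a Mann-Whitney difference test that cannot show equivalence.* The normality switch is stated for data in general, and a later sentence assigns equivalence tests to the primary outcomes. Whether the switch also governs them is unclear. Rank-based equivalence procedures exist; the plan simply specifies none. How often a normality test would fail depends on an assumed distribution and spread, and carries no weight here.
- *That a margin has been or will be chosen or widened after seeing results.* Nothing in the documents shows this. The point is that nothing in them prevents it.
- *That open treatment threatens all outcomes equally.* Knowledge of the arm mainly affects pain scores and opioid use. Concentration is a laboratory measurement, for which the remaining risk is a late choice of margin, sample or fraction.

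**Conclusion.** The concern holds and should be fixed before any comparison by arm. As written, the plan cannot deliver an equivalence conclusion, because the primary outcome, its summary and time point, the between-arm margin and the decision rule are all absent. The test therefore has no defined null, and the superiority fallback has no trigger.

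On size, 70 patients give 80% power for a margin of about 0.71 SD at one-sided 0.05, so adequacy turns on a margin nobody has stated. This rests on assumed 1:1 allocation, no loss and zero true difference. The missing elements themselves rest on no assumption.

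**What to change.** In V.iii and VIII, before any comparison by arm:

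1. Name the primary outcome with its summary measure and time point. For lidocaine, say whether free or total drug is used and which samples count as steady state. State the margin, SD, α and power entered in the calculator. If they cannot be recovered, set the margin on stated clinical grounds and report the power that 70 patients give under stated SD and attrition assumptions.
2. Conclude equivalence only if the confidence interval for the arm difference lies wholly inside the margin: a 90% interval for one-sided 5%, or a 95% interval if the calculator used one-sided 2.5%. Define failure as not meeting this rule, and state that a non-significant difference test is not evidence of equivalence.
3. If concentration is a primary outcome, analyse it on the log scale as a geometric mean ratio with its interval against a ratio margin set in advance, instead of letting a normality test choose the method. A prespecified rank-based or untransformed equivalence test would also close the gap; the log scale is the usual choice for concentrations.
4. If more than one primary outcome is kept, say whether all must pass.

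The cost is wording, with no new patient data. If the inputs are lost, an SD must be assumed and justified, because the documents give none. A fixed margin may make the claim harder to reach: anything tighter than about 0.71 SD (0.75 to 0.79 SD with 10 to 20% loss) has under 80% power at one-sided 0.05. On the log scale, the margin for 80% power with 35 per arm is exp(±0.7066 × √ln(1 + CV²)). That is a ratio of 0.81 to 1.23, 0.76 to 1.31 or 0.72 to 1.40 for an assumed between-patient CV of 30%, 40% or 50%.
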